Since it was first introduced into the United States in the late 90's, UFE has presented women with a non-surgical, minimally invasive, and uterine-sparing option for the treatment of their symptomatic fibroids [12]. Since then, multiple randomized controlled trials (RCTs) have shown similar efficacy of UFE compared to hysterectomy. One of the initial studies, the EMbolization versus hysterectoMY (EMMY) trial, found that patients recovered and returned to work significantly sooner in the UFE cohort, and that there was no difference in symptom relief at 2 years between the two groups [13-15]. Other studies, such as the Randomized Trial of Embolization versus Surgical Treatment for Fibroids (REST) found that UFE patients recovered more quickly and had less pain than surgery patients. At 1 year, both groups had similar degrees of improvement in health-related quality of life and had similar levels of satisfaction. A third study, found that patients who underwent UFE rather than hysterectomy additionally had a shorter hospital stay, thus highlighting some of the financial benefits of UFE [16]. Further, several clinical trials have shown an increased complication rate and lower patient satisfaction scores for those women who underwent hysterectomy for the treatment of their fibroids, as opposed to Uterine Artery Embolization (UFE) [17, 18].

One of the major side effects of UFE is the pain and cramping that patients experience after the procedure, which is most pronounced in the first 12-24 hours. Therefore, much interest has been placed on determining what causes pain following UFE and how best to alleviate it. Some studies have addressed the timing and nature of post-UFE pain, with a finding that the initial pain is due to uterine myometrial ischemia [19, 20]. Later at about 72 hours, some patients begin to report loss of appetite, nausea, vomiting, and fatigue - a constellation of symptoms termed post-embolization syndrome (PES). PES can lead to readmission in up to 10% of patients [2]. Hence, there appears to be two distinct phases of pain in the post-UFE patient: 1. The immediate ischemic pain, and later, 2. The PES symptom constellation.

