- *Pain, nausea, vomiting and fever will be documented using the visual analog score and nausea and vomiting score at:*
 - *Time 0 Immediately prior to the procedure*
 - *1 hour intervals for the first 3 hours*
 - *3 hour intervals for the next 9 hours*
 - *6 hour intervals for the next 12 hours*
 - *Daily, for the next 3 days*
 - *Once at day 7*
- *Each patient will complete uterine fibroid symptom & health-related quality of life questionnaire prior to the procedure and then 1 month and 3 month after.*
- Each patient will undergo post-procedural MRI imaging to determine residual fibroid burden and approximate volume at 3 months in order to gauge treatment response.
- PCA usage statistics.

Study Design:

This study is designed as a double blinded, placebo controlled randomized control trial. As previously mentioned, the study will divide the patients into two groups. The test group will receive intra-procedural intra-arterial dexamethasone and the control group, a saline placebo. Block randomization (Size: 8) will be done using a random number generator.

The drug or placebo will be prepared by research pharmacy and be delivered to the Interventional Radiology Department in identical containers with specific serial numbers. The physician performing the UFE, the patient and the research team will be unaware of the nature of the administered drug/placebo or the patient grouping. The drug preparation will be coordinated by the University of Miami Pharmacy Department's Research Coordinator, [name]. Once the uterine artery is catheterized, the drug or placebo will be injected intra-arterially. Embolization is then performed as usual.

Following UFE, all patients will be admitted to the general inpatient unit for observation, as is standard of care for all UFE patients. Following this observation period, patients will be discharged with appropriate instructions of when and how to follow-up with the treatment team. This will include explicit instructions to self-monitoring for unusual bleeding, swelling, bruising at the femoral artery access site, abnormal uterine bleeding, cramping, extended bouts of nausea, vomiting, fever, chills, and malaise. All patients will be given the number of an on-call physician for questions and concerns they may have. As mentioned above, all patients will be telephoned daily by a member of the research team on day 2, 3, 4, and 7 post-UFE.

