A single computer system managed by the Pharmacology Research Coordinator, [name], will be maintained to ensure blinding of the cohorts. Collected data will be analyzed by [name], and done so prior to unblinding.

16. Provisions to Monitor the Data to Ensure the Safety of Subjects*

All data will be analyzed as it arrives and on a rolling basis by the primary physicians and researchers directly involved in this study, to ensure that the clinical findings and participant reported responses to the Pain & UFE Survey are not deviating in a way that could lead to undue harm.

As stated previously, all participants will be admitted to the hospital for observation for the first 24 hours and discharged with 2-week clinical follow-up in place and the contact information of a research team member. All participants will be contacted daily for the first 3 days, then at 7 and 14 days following the procedure. Any adverse effects of safety issues would be discovered in this follow up.

At 6 months we will analyze the interim data for any difference in the efficacy of treatment between the groups. All data will be analyzed using IBM SPSS software. We will use Student's T test for analysis of continuous variables, Chi square test for categorical variables with significance level set at two tailed p value of <0.05.

Although we expect that this trial exposes the participants to minimal risk, we consider the following statistically-significant differences between the two arms to be grounds for immediate trial termination: excessive abnormal uterine bleeding, infection, and sepsis.

17. Withdrawal of Subjects*

Subjects will be immediately withdrawn if it is deemed at any time prior to the procedure date that they fall into any of the previously outlined Exclusion criteria, suffer an intra-procedural adverse reaction to the use of dexamethasone, or willingly choose to leave the trial at any time.

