All imaging findings, diagnostic studies, complications, and follow-up treatments will be shared with both patient and their appointed primary care/obstetrics physicians. However, the study will remain blinded to both patient and clinician until the study is deemed closed, an adverse event occurs, or the study is prematurely terminated for any of the reasons previously stated. Any shared health information will be done so utilizing HIPAA-compliant channels.

24. Setting

Recruitment will occur in our already-established Interventional Radiology clinics located at University of Miami, at the professional arts center (PAC). Likewise, UFE procedures will be carried out at University of Miami Health Towers or University of Miami Hospital and Clinics or Lennar Foundation Medical center, utilizing similar or identical equipment and the previously stated methods. Data analysis will

be carried out on University of Miami computer systems on a rolling basis to ensure participants are not placed at undue risk.

25. Resources Available

The below members will meet monthly and on an as-needed basis, share all data via a University-approved means, a shared Box folder. This will include this IRB proposal, the Study Consent Form, the Patient Information Packet, and a data spreadsheet to compile the UFE Pain & PES Survey scores. The Principal Investigator shall have the responsibility of coordinating the study effort, and together with the Participating Physicians shall be responsible for the UFE procedures and the monitoring of study participants to ensure safety. This will include coordination between the Advanced Care Practitioners and the Research Coordinator to monitor for any participant adverse events. The Clinical Pharmacist will be responsible for compounding the Dexamethasone and Saline placebo, as well as blinding the study by assigning serial numbers to the medicine vials.

Principal Investigator:

[name]

Associate Professor - Clinical Interventional Radiology

Program Director for the Interventional Radiology Residency and Fellowship

Co-investigators:

[name]

Chairman, Department of Vascular and Interventional Radiology

Associate Professor of Interventional Radiology and Urology

[name]

Associate Professor of Vascular and Interventional Radiology

[name]

Assistant Professor, Department of Obstetrics and Gynecology

[name]

Assistant Professor of Vascular and Interventional Radiology

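### Section 23 ends the blind of patient and clinician at any adverse event, with no stated limit, so later self-rated scores could be given by patients who know their arm

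*Combined protocol and SAP*

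**What the plan says.** Section 23 (Sharing of Results with Subjects) sets how long the blind lasts: "the study will remain blinded to both patient and clinician until the study is deemed closed, an adverse event occurs", or the study ends early for reasons given before. The closing qualifier about earlier reasons reads naturally with early termination, not with the adverse event.

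Other sections describe the blinding without this exception:

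- Section 13, Study Design: "The physician performing the UFE, the patient and the research team will be unaware of the nature of the administered drug/placebo".
- Section 15: a pharmacy-managed computer system "will be maintained to ensure blinding of the cohorts", with the data analysis "done so prior to unblinding".

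The search for adverse effects is in Section 16. Patients are observed in hospital for 24 hours, and then "All participants will be contacted daily for the first 3 days, then at 7 and 14 days following the procedure". Section 13 gives the survey calls slightly differently: "all patients will be telephoned daily by a member of the research team on day 2, 3, 4, and 7 post-UFE". Pain, nausea and vomiting are scored by the patient up to day 7. The quality-of-life survey is completed before the procedure and at 1 and 3 months.

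The nearest thing to a threshold is in Section 11, which speaks of severe events related to the modified procedure. It does so only as a condition for completing enrollment and analysis, not for unblinding.

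**The concern.** An unblinding exception is normal in a double-blind trial. The problem is that this one has no limit. The available text gives no severity, relatedness or need criterion. It does not say who decides or who is told, whether one patient or more are affected, or how scores recorded afterwards are handled. Staff who followed Section 23 literally would depart from Sections 13 and 15.

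The trigger could be met often. Section 18 lists pain, bleeding and infection among the known complications of the procedure, so a symptom that the trial measures as an outcome could itself count as an adverse event.

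The outcomes at stake are mostly self-rated. A patient who learns her arm may score later symptoms partly by expectation, and the t-test in Section 16 would count that shift as drug effect. The exposure grows with time:

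- **Early pain:** least exposed. Section 7 says of post-procedure pain, "which is most pronounced in the first 12-24 hours". Protection is not complete, because an event during the admission could unblind a patient while pain is at its peak.
- **PES (aim 2):** more exposed. Section 7 says, "Later at about 72 hours, some patients begin to report loss of appetite, nausea, vomiting, and fatigue".
- **Quality of life (part of aim 3):** most exposed, since both post-procedure surveys come after every safety contact.
- **Fibroid volume on MRI (also aim 3):** not self-rated, so not open to this bias.

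**Working it through.** **Inputs from the documents.** Section 9: means 2.89 (SD 1.09) and 3.91 (SD 2), effect enlarged by 50%, 21 per group, significance level 0.05, stated power 86%. Section 16: two-tailed test. Section 13: the scoring schedule.

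**Reproducing the plan's figure.**
- Planned difference = 1.5 × (3.91 − 2.89) = 1.53 points.
- Pooled SD = √((1.09² + 2²)/2) = 1.611.
- Standard error = 1.611 × √(2/21) = 0.497.
- Power = 86.8% by the normal approximation and 85.2% by noncentral t with 40 degrees of freedom.

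Both agree with 86% to within a point, so the same model is used below.

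**Which scores can follow an event.** Post-procedure pain scores fall at 1, 2, 3, 6, 9, 12, 18 and 24 hours and, with the Section 13 calls, at days 2, 3, 4 and 7. That is 12 scores, 8 of them within 24 hours. The 4 later ones coincide with calls at which an event may come to light.

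**Size of the bias.** The documents give no overall adverse-event rate and no size for an expectation effect. The only rate of a related kind is PES readmission in up to 10% of patients (Section 7). If every such readmission counted as an event, 42 × 0.10 = 4.2 patients would be affected, and the chance of at least one is 1 − 0.9⁴² = 98.8%.

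Assume a share f of patients is unblinded, the same in both arms, and that the difference between arms moves by 1 point in favour of the drug among their affected scores. Bias = f × 1 × w, where w is the share of the analysed score recorded after unblinding. Type I error comes from noncentral t (40 degrees of freedom, noncentrality = bias/0.497), with no true effect and the same SD for single and averaged scores.

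| Analysed pain score | w | f = 10% | f = 30% | f = 50% |
|---|---|---|---|---|
| Mean of all 12, only the 4 after 24 h shifted | 4/12 | bias 0.03; 5.0% | 0.10; 5.4% | 0.17; 6.2% |
| Mean of the 4 late scores, event found at the day 2 call | 3/4 | 0.08; 5.2% | 0.23; 7.3% | 0.38; 11.4% |
| Score wholly after unblinding | 1 | 0.10; 5.4% | 0.30; 9.1% | 0.50; 16.6% |

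A score taken wholly before unblinding has w = 0, no bias and a type I error of 5%. That is the lower bound. Section 12 names no time point for the primary pain score, so the documents do not say which row applies.

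**Sensitivity to the assumed shift.** In the last row, shifts of 0.5 and 2 points give 5.1% and 6.8% at f = 10%, and 6.0% and 21.8% at f = 30%.

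**PES and quality of life.** The documents give no SD. In SD units with w = 1, a shift of 0.25 SD gives 5.1% and a shift of 0.5 SD gives 5.3% at f = 10%. At f = 50% the figures are 6.8% and 12.4%.

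**The case against.** The strongest reply is that this is loose wording and not an operating rule. The clause is part of one sentence in a section on sharing results. The blinding design is in Sections 13 and 15, and both point to keeping the blind. The Section 11 wording suggests the authors had severe, related events in mind. Section 17 withdraws patients who react to dexamethasone during the procedure, so some of the likeliest code-breaks may add no later scores. The unseen appendices may already set a limit. At 10% unblinded the effect on pain is negligible.

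Much of this stands. It supports reading the clause as an oversight and keeps the likely numerical effect small. It does not remove the conflict: Section 23 states when the blind ends, the Section 11 wording is not attached to it, and neither Section 13 nor Section 15 restricts it.

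A reader might also infer more than the documents support:

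- **That one event unblinds the whole trial.** The grammatical subject is the study, so the words allow it. But the pharmacy-held system, the individually numbered vials or syringes and the planned analysis before unblinding all point the other way.
- **That the trial is not truly double-blind, or that its pain result is unreliable.** An exception is compatible with a double-blind design, and 8 of the 12 post-procedure pain scores are taken within 24 hours.
- **That type I error is materially inflated.** The larger figures need 30% or 50% of patients unblinded, or a 2-point shift. No passage supports any of these.

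**Conclusion.** The point holds as a defect of wording with a real but probably small consequence. Section 23 makes any adverse event end the blind of patient and clinician. The available text sets no limit, and Sections 13 and 15 say otherwise. It should be corrected, because the outcomes are mainly self-rated and correction costs little.

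The size cannot be determined from the documents. With 10% unblinded and a 1-point shift, the type I error for pain is 5.0% to 5.4%, and scores before unblinding are unaffected. The values of 9.1% and 16.6% are upper cases that need 30% or 50% unblinded and an analysed score falling wholly afterwards. The unblinded shares, the shift and the common SD are assumptions. Confidence is medium, because the consent form and General Trial Protocol might already contain the limit.

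**What to change.** Redraft the Section 23 sentence along these lines:

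> Patients and clinicians will remain blinded until the study is closed or prematurely terminated. If an adverse event requires it, under a criterion the sponsor states, the code may be broken for the affected patient only; all other patients, the research team members collecting scores and the analyst remain blinded.

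The sponsor should supply the criterion and say who is told. Then add:

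1. The research pharmacy logs each code-break with its date and reason. It already keeps the serial-number log (Section 36).
2. Code-breaks are reported by arm.
3. A sensitivity analysis of the self-rated outcomes excludes scores recorded after a code-break. It should accompany the main analysis and not replace it, since patients with events may differ between arms.

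Sections 13, 15, 16 and 23 should be reconciled with this wording. If an appendix already sets the limit, a cross-reference in Section 23 can take the place of a new criterion.

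The cost is protocol wording, a short log and one extra analysis. Visits, sample size and treatment do not change.
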